6.1.6. Pooling of Sites

Sites with < 2 participants in any treatment arm at Week 52 will be pooled into a common site. All sites with ≥ 2 participants in both treatment arms at Week 52 will not be pooled.

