This statistical analysis plan (SAP) describes the planned analysis and reporting for Cassava Sciences' protocol PTI-125-07, one of two Phase 3 protocols designed to provide safety and efficacy data for simufilam, a novel small molecule drug, in support of a New Drug Application filing for the treatment of mild-to-moderate Alzheimer's Disease (AD) dementia.

Protocol PTI-125-07 is a registrational Phase 3 study being conducted under a Food and Drug Administration (FDA) Special Protocol Assessment (SPA) dated August 2021. An SPA documents FDA's agreement that the design and planned analysis of a study can adequately address objectives in support of a regulatory submission.

PTI-125-07 is titled: *A Phase 3, Randomized, Double-Blind, Placebo-Controlled, Parallel-Group, 52-Week Study Evaluating the Safety and Efficacy of Simufilam 100 mg Tablets in Subjects with Mild-to-Moderate Alzheimer's Disease*, dated 15-FEB-2023 ([version 3.0](#)).

Reference materials for this SAP include the protocol and the accompanying sample data collection documents. Operational aspects related to collection and timing of planned clinical assessments are not repeated in this SAP unless relevant to the planned analysis.

The structure and content of this SAP provides sufficient detail to meet the requirements identified by the FDA, European Medicines Agency (EMA), and International Conference on Harmonization (ICH) of Technical Requirements for Registration of Pharmaceuticals for Human Use: ICH Topic E9 Statistical Principles for Clinical Trials ([ICH, 1998](#)) and the addendum R1 (ICH, 2020). All work planned and reported for this SAP will follow internationally accepted guidelines, published by the American Statistical Association (ASA, 2022) and the Royal Statistical Society ([RSS, 2014](#)), for statistical practice.

The planned analyses identified in this SAP may be included in clinical study reports (CSRs), regulatory submissions, or future manuscripts. Post-hoc exploratory analyses not necessarily identified in this SAP may be performed to further examine study data. Any post-hoc or unplanned, exploratory analysis performed will be clearly identified as such in the final CSR.

The statistical plan described hereafter is an *a priori* plan. It will be approved before any unblinded inferential or descriptive analysis of data pertaining to Cassava Sciences' study PTI-125-07.

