2.5. Method of Assigning Participants to Treatment Groups

The randomization schedule was computer generated by an independent statistician and randomly allocated each treatment to randomization numbers. The randomization numbers were assigned sequentially through a central interactive response technology (IRT) system as participants entered the study. The randomization was stratified as described in section 2.4.

The randomization schedule will not be revealed to participants, clinical investigators, clinical staff, study monitors, statistical personnel or Cassava Sciences until all participants have completed treatment and the database has been finalized and locked.

Participants who discontinue from the study or are terminated will not be replaced.

The IRT system will be used throughout the study for screening, randomization, study drug dispensation and management, and emergency unblinding. Individual participant treatment is automatically assigned by the IRT at baseline (Study Day 1) to participants who meet all entry criteria. The participant's randomization number is a unique number corresponding to the treatment allocated to the participant.

At each dosing visit, the site will access the IRT system, and enter the necessary participant-specific information. For randomized participants, this information is used by the IRT system to dispense the correct dose and amount of study drug in a uniquely numbered bottle.

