4.3. Interim Analysis and Data Monitoring

No interim efficacy analyses or sample size re-estimations were conducted.

An external DSMB will be involved in the management of this study. The DSMB meeting will be held periodically for the duration of the study. The purpose of the DSMB is to review the progress of the study with special regard to safety and make recommendations to the Sponsor on how to handle any safety concerns that arise. Further details regarding the DSMB can be found in the DSMB charter which was finalized before the first meeting was scheduled.

5. Analysis Populations

The following analysis sets are planned for this study:

- **Intent-To-Treat (ITT) Analysis Set:** The ITT analysis set includes all randomized participants. The primary efficacy analysis will be based on this analysis set.
- **Intent-To-Treat (ITT-mild) Analysis Set:** The ITT-mild analysis set includes all randomized participants who have a baseline MMSE of 21-27.
- **Safety Analysis Set (SAF):** The SAF analysis set includes all participants who received at least one dose of study treatment. All safety analyses will be completed in the SAF analysis set and participants will be included in the group based on the treatment received.
- **PK sub-study Analysis Set:** The PK sub-study analysis set includes all participants who sign the PK consent and/or re-consent form and have at least one non-missing post baseline PK assessment available.

Assignment of participants to analysis sets will be confirmed at a blinded data review meeting to be held before the study database is locked.

6. General Issues for Statistical Analysis

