6.1.2. Adjustments for Covariates

Efficacy analyses will include as covariates the baseline value of the endpoint being analyzed and the MMSE baseline score, along with the interaction of these covariates with Visit. Investigative site (pooled, see section 6.1.6) will also be included as a categorical fixed effect.

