6.1.4. Handling of Dropouts or Missing Data

Although every attempt will be made to ensure participants remain in the study to completion and all data is collected as scheduled, the occurrence of missing data cannot be completely prevented.

An incomplete start or stop date of an AE or a medication will be imputed as described in section 6.1.8.

Any participant who withdraws from the study will be considered to have missing data at all subsequent visits. The primary analytic approach for efficacy assumes missing at random (MAR) to estimate what would have been observed if the participant had not discontinued. A reference-based multiple imputation sensitivity analysis (copy reference) will be employed in which missing not at random is assumed such that after discontinuation, drug-treated participants will have placebo-like values imputed for their missing data.

If up to two individual items of the total 12 items for the ADAS-Cog12 (maximum score = 80) are missing for non-cognitive reasons, the total score will be imputed by multiplying the observed score (i.e. the score for the non-missing items) by a factor that includes the maximum scores for the missing item(s) as follows:

$$\text{Imputed score} = \text{Observed score} * (80/[80-\text{maximum score for missing items}]).$$

As an example, if the first item “Word Recall” (maximum score = 10) and the second item “Commands” (maximum score = 5) are missing, the observed score will be multiplied by the factor $80/(80-[10+5])$ or $80/65$ or 1.23. The imputed score will be rounded to the nearest integer. ADAS-Cog12 tests with more than two missing items will be considered missing scores.

Missing items on other assessments will not be imputed; such scores will be considered missing.

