8.1. Co-Primary Efficacy Analysis

Visit wise mean changes from baseline will be analyzed in the ITT analysis set using a restricted maximum likelihood (REML)-based repeated measures approach (MMRM). The MMRM analysis assumes a missing at random (MAR) missing-data mechanism, meaning that drop out is related to observed outcomes of the dependent variable and covariates, but not to the unobserved outcomes. The analysis will include the categorical, fixed effects of treatment group, visit, and pooled site, along with the continuous, fixed covariates of baseline value of the endpoint being analyzed (baseline), baseline MMSE score, and the interactions of treatment group, baseline, and baseline MMSE with visit. An unstructured (co)variance structure will be used to model the within-participant errors. If this analysis fails to converge, the following structures will be tested in this order, with the first structure yielding convergence to be used as the appropriate structure for that variable: heterogeneous Toeplitz, heterogeneous compound symmetric, and compound symmetric. If one of the structures other than unstructured is used, variance of the Maximum Likelihood Estimator (MLE) will be based on the Sandwich Estimator (empirical option in PROC MIXED statement). If none of the structures yield convergence, site will be removed from the model and the sequence of covariance structures will be refit as described above. The Kenward-Roger approximation will be used to estimate denominator degrees of freedom.

Significance tests for the between-treatment group differences will use a two-sided 0.05 level, with the primary analysis based on the ITT analysis set.

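### Pooled site in the primary model is defined by arm-specific counts at Week 52, so it depends on retention and the site map cannot be drawn up under blind; the expected effect is small and the remedy is cheap

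*SAP*

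**What the plan says.** SAP 6.1.6 gives a two-sentence rule: "Sites with < 2 participants in any treatment arm at Week 52 will be pooled into a common site", and "All sites with ≥ 2 participants in both treatment arms at Week 52 will not be pooled". SAP 6.1.2 applies it to the efficacy models: "Investigative site (pooled, see section 6.1.6) will also be included as a categorical fixed effect". SAP 8.1 repeats it for the co-primary MMRM: "The analysis will include the categorical, fixed effects of treatment group, visit, and pooled site". Sections 8.2 and 8.4 carry pooled site into the secondary MMRMs, the CDR-SB ANCOVA and the subgroup models. The CMH responder and progression analyses in 8.5 and 8.6 have no site term. The primary model in protocol 11.3.1 has none either, so pooled site is an addition made by the SAP.

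Three other places bear on timing:

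- SAP 6.1.4 on withdrawal: "Any participant who withdraws from the study will be considered to have missing data at all subsequent visits".
- SAP 2.5 withholds the randomisation schedule from, among others, "statistical personnel or Cassava Sciences until all participants have completed treatment and the database has been finalized and locked".
- SAP Section 5 on the blinded review: "Assignment of participants to analysis sets will be confirmed at a blinded data review meeting to be held before the study database is locked". It mentions analysis sets only, not site pooling.

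**The concern.** Adjustment factors in a primary model are normally fixed by what is known at randomisation. Here, whether a site stands alone or joins the common pool depends on how many of its participants remain in each arm a year later. If retention differs by arm, treatment helps to define a covariate used to estimate the treatment effect.

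The mechanism for bias is specific. Suppose active-arm dropout is heavier at sites where participants do worse (or better). Those sites lose their second active participant and are pooled. Inside the common level, the remaining active and placebo participants then come from a different mix of sites, and the single pooled intercept cannot adjust for that.

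The second issue is procedural. The rule needs counts by arm, so nobody blinded can list the pooled sites before lock. For a registration study this is an avoidable criticism of the primary model.

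**Working it through.** **The plan's own figure.** SAP 2.2 gives a placebo change of 5.0, a 45% difference, SD 8.5, two-sided 0.05 and 90% power.

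- Effect: 0.45 × 5.0 = 2.25 points.
- n per arm: 2 × (1.960 + 1.282)² × 8.5² / 2.25² ≈ 300. Power at 300 is 0.900.
- With 20% dropout: 300 / 0.80 = 375 per arm.

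The stated sample size reproduces and is not affected by this point. The planning standard error is 8.5 × √(2/300) = 0.69 points. The documents give no figure for site pooling itself.

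**How close sites lie to the threshold.** SAP 2.2 and 2.3 give 804 randomised at about 77 sites: 804 / 77 = 10.4 per site, 5.2 per arm, and 5.2 × 0.8 ≈ 4.2 per arm at Week 52. Smaller sites therefore sit near the cut-off of 2.

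**How many sites the timing of the count moves.** Simulation with 77 sites, 804 participants, 1:1 allocation and 20% dropout in both arms. The site-size distributions are assumptions.

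| Site sizes | Pooled on randomised counts by arm | Pooled on Week 52 counts by arm |
|---|---|---|
| Equal expected size | 5 | 12 |
| Moderately skewed | 19 | 25 |
| Strongly skewed | 23 | 28 |

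With dropout varied from 10% to 30% by arm, about 2 to 8 sites change status through retention alone.

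**Effect on the estimate.** Completer ANCOVA under the null, comparing the two timings of the by-arm count:

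- Site SD 2, equal 20% dropout: mean estimates differ by less than 0.001 points. Rejection is 5.4% (Week 52) and 6.0% (randomised), with Monte Carlo error of about 0.4 percentage points.
- Site SD 2, 10% against 30% dropout, related to site and to an earlier score in the same way in both arms: the mean shifts by about 0.02 points. Rejection is 5.5% (Week 52) and 5.3% (randomised).
- 10% against 30% dropout, with active-arm dropout related to site level: bias is about 0.11 points (site SD 2), rising to 0.49 in an extreme case (site SD 4), against about 0.01 to 0.15 under randomised counts.

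Across the scenarios the two estimates in a single trial differ with an SD of about 0.08 to 0.12 points, which is 0.08/0.69 ≈ 12% to 0.12/0.69 ≈ 17% of the planning standard error. With an assumed site SD of 1.5, the conclusion at 0.05 differed between the rules in 0.8% of trials (null), 1.2% (effect 2.25), 2.8% (null, differential dropout) and 4.2% (effect 1.4).

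**Whether the map can be frozen.** The rule needs counts by arm, and SAP 2.5 keeps the schedule closed until lock. No section asks an independent party to supply a pooling list. A rule on randomised counts by arm has the same difficulty; only a count that ignores arm avoids it.

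**What the text leaves open.** The SAP does not say whether being present at Week 52 means remaining in the study or having a value of the endpoint. On the second reading the site factor could differ between ADAS-Cog12, where up to two missing items are imputed, and ADCS-ADL, where none are (6.1.4). Nor does it say whether pooling is redone in ITT-mild.

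**The case against.** The rule is written down in a SAP of which Section 1 says: "It will be approved before any unblinded inferential or descriptive analysis of data". Its two sentences classify every site, so once the Week 52 count is defined no discretion remains. A reader might infer that the analyst can choose the site map after seeing results, or that the primary analysis is not pre-specified. The documents do not support that: what waits for the codes is the output of a fixed rule.

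The factor is a coarsening of site, which is a baseline attribute. All participants at a site share one level, nobody leaves the ITT set, and 8.1 has no treatment-by-site term. It is not an individual post-randomisation covariate, and this fits the near-zero bias in most scenarios.

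The Week 52 count also has a purpose. The primary contrast is at Week 52, and the rule ensures that each stand-alone site has at least 2 participants per arm there. Section 8.1 already foresees convergence trouble and drops site as a last resort, so sparse levels are a legitimate worry. This stands, and it means that the change has a cost.

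A reader might also take the 1 to 4% of trials with a changed conclusion as evidence of error inflation. It is not. Two similar adjustment sets will disagree occasionally near the boundary, and the rejection rates show no detectable difference.

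**Conclusion.** The point holds as a weakness of covariate definition. The pooled-site factor depends on arm-specific retention, and its levels cannot be listed under blind. It does not show that the primary result is biased or that type I error is inflated. It also does not reach every efficacy analysis, since the CMH tests have no site term.

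The size is small. Without a link between dropout and site, nothing is detectable. Bias of about 0.11 points (0.11/2.25 ≈ 5% of the planned effect) needs both differential dropout and active-arm dropout related to site level. The 0.49-point case (about 22%) rests on a deliberately extreme site SD. Site sizes, site SD and dropout by arm are all assumptions. The calculations use ANCOVA on completers, whereas in the SAP's MMRM dropouts contribute their earlier visits. The change is a cheap improvement, not a necessary correction.

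**What to change.** Before database lock, amend SAP 6.1.6 so that pooling uses the total number randomised at each site regardless of arm; for example, sites with fewer than 4 randomised form the common site. Confirm and freeze the site list at the blinded data review, and state that the same list applies in all efficacy models with a site term, for both co-primary endpoints, ITT-mild and the sensitivity analyses. This also removes the need to define presence at Week 52.

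Changing only the timing, from Week 52 to randomised counts by arm, would remove the dependence on retention but would still need treatment codes.

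The cost is one dated SAP revision. A few stand-alone sites may then have fewer than 2 participants in an arm at Week 52 and add little to the contrast. The standard error would be roughly 0.5 to 1.5% larger; a low threshold leaves more small sites separate and could cost slightly more. Because the model has main effects of site only, the treatment contrast remains estimable.

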6.1.7. Derived Variables and Conventions

Age: the age at baseline will be used.

Alzheimer's disease status

- MMSE = 21-27 (mild dementia)

- MMSE = 16-20 (moderate dementia)

Change from baseline = post-baseline value at timepoint – value at baseline

Time since diagnosis of AD (months) = (date of first dose – date of diagnosis) / 30.4375

Treatment duration (days) = (date of last dose of study drug – date of first dose of study drug) +1

Study Drug Exposure = treatment duration (days), that is the number of days a participant is on study drug will be calculated as the number of days from date of first dose to date of last dose plus 1.

Study Drug Compliance (%) = 100 x Total number of tablets taken / Total number of expected tablets. That is, study medication compliance will be calculated based on the numbers of tablets dispensed minus the number of tablets returned divided by the expected number of tablets based on the duration of the participant's participation in the study.

Study drug compliance will not be calculated for participants whose date of last study drug is unknown.

Total Dose (mg) = $\sum [\text{Number of doses taken}_i \times \text{Dose received (mg)}_i]$

where,

$i = 1$ to k , (k = number of time periods participant is receiving a constant dose)

Average Daily Dose (mg/day) = Total Dose (mg) / Treatment Duration (days)

Dose variables (dose, total dose, and average daily dose) not calculated for placebo participants.

The iADRS for this trial is a composite endpoint that combines scores from the 12-item AD Assessment Scale-Cognitive subscale (ADAS-Cog12) and the AD Cooperative Study - instrumental Activities of Daily Living (ADCS-iADL). The ADCS-iADL is defined as items 6a and 7-23 of the ADCS-ADL.

iADRS score = $[-1(\text{ADAS-Cog12}) + 80] + \text{ADCS-iADL}$

6.1.8. Data Adjustments/Handling/Conventions

All collected data will be presented in listings or Clinical Data Interchange Standards Consortium (CDISC) datasets. Analysis results will be presented and summarized in either tables and/or figures. Data not participant to analysis according to this plan will not appear in any tables or graphs but will be included in the data listings.

All p-values will be displayed in four decimals and rounded using standard scientific notation (e.g., 0.XXXX). If a *p-value* less than 0.0001 occurs, it will be shown in tables as < 0.0001.

The version 24.0 of the Medical Dictionary for Regulatory Activities (MedDRA) will be used to classify all AEs by system organ class (SOC) and preferred term (PT).

Prior and concomitant medications will be classified using Anatomical Therapeutic Chemical class (ATC level 2) and preferred term (ATC level 4) from World Health Organization Drug Dictionary (WHO-DD), WHODrug Global B3 version March2021.

Medications that start before the first dose of study drug are considered prior medications whether or not they were stopped prior to the first dose of study drug. Any medication continuing or starting on or after the first dose of study drug will be considered as concomitant. If a medication starts prior to the first dose of study drug and continues after the first dose of study drug, the medication will be considered as both prior and concomitant.

Adverse events or medications with entirely missing start dates will be classified as treatment-emergent or concomitant, as appropriate.

For partial AE or medication start dates: (a) if only the day is missing, and the month and year match the first dose date and the end date is on or after the first dose date, or AE/medication is ongoing, then the date is assigned the first dose date thus the event/medication will be considered as treatment-emergent/concomitant; if the month and/or year do not match the first dose date or the end date is prior to the first dose date, then the day is assigned the first day of the month (01); (b) if month or the day and month are missing, and the year matches the first dose date and the end date is on or after the first dose date, or AE/medication is ongoing, then the date is assigned the first dose date; if the year does not match the first dose date or the end date is prior to the first dose date, then the day/month are assigned the first day of the year (01JAN).

For partial end dates: (a) if only the day is missing, then the day is assigned the last day of the month; (b) if both day and month are missing, they are assigned the last day of the year (31DEC).

For analysis purposes, repeat laboratory results will not be used unless the original value is indicated as missing or invalid. In such cases, the first non-missing repeat value will be used for data analysis. The international system of units (SI) will be used in reporting all laboratory values.

Participants will be analyzed by the treatment received for all safety and tolerability assessments.

Participants are stratified through the IRT system based upon MMSE score entered. Once an MMSE score is entered, that participant is randomized to either high MMSE (21-27) or low MMSE (16-20) strata. At study start, it was decided to stratify participants in this manner so there would be a balance in the number of participants on placebo vs active drug (and within treatment arms) within each stratum. The stratification of the participants does not impact their probability of being assigned to different treatment arms. Once randomized through IRT, the MMSE score and the stratification assigned cannot be changed.

For instances where the MMSE score was incorrectly entered into IRT, the MMSE score given by the vendor will be used to calculate the strata for safety and efficacy analyses if there are any subgroup analyses.

All collected data will be presented in listings. Data not subject to analysis according to this plan will not appear in any tables or graphs but will be included only in the data listings.

A treatment related AE is any AE with a relationship to the study drug of *“Possibly Related”* or *“Probably Related”* or *“Reasonable Possibility”*.

If partial dates occur, the convention for replacing missing dates for the purpose of statistical analysis is as follows: if just day is missing then the day assigned is the first day of the month or the date of first dose (if in the same month), whichever is later; if just month is missing then the month assigned is the month of the first dose, unless that results in a date before the first dose in which case the month after the first dose is used; and if both month and day are missing then the month assigned is the month of the first dose and the day assigned is either the first day of the month or the first dose date, whichever is later.

If partial times occur, the convention is as follows: if the missing time occurs on the day of the first dose and both the hour and minute are missing then the time assigned is the time of the first dose, otherwise if both the hour and minute are missing and the date is not the date of first dose the time assigned is 12:00; if the date is the same as the date of the first dose and only hour is missing the hour assigned is 12 or the hour of first dose, whichever is later, and if the date is the same as the date of first dose and only the minute is missing the minute assigned is 30 or the minute of first dose, whichever is later. Otherwise, the hour assigned is 12 if the hour is missing and the date is not the same as the date of first dose and the minute assigned is 30 is the date is not the same as the date of first dose.

These conventions will be applied only to adverse event onset dates and times with the following precaution: if the missing date and time reflect the date and time of onset of an adverse event, the modified date and time will be constructed to match the first documented date/time post drug administration while preserving the order in which the AE was reported in the CRF.

7. Study Participants and Demographics

Participant disposition, demographics and other baseline characteristics, prior medications, and study drug exposure and compliance will be summarized by randomized treatment group and overall, using the ITT analysis set, unless otherwise specified below in each section.

